## **2. Design**

DISC is a multi-centre, parallel group, individually randomised controlled non-inferiority trial of collagenase injection and manipulation versus limited fasciectomy surgery for the treatment of Dupuytren's contracture. In addition to the main study, DISC contains a qualitative sub study and a photography sub study. This plan outlines the pre-specified analyses of the main trial and the photography sub study. Eligible and consenting patients will be randomised 1:1 to either collagenase injection and manipulation or limited fasciectomy surgery, using a secure randomisation service. Due to the nature of the interventions under investigation, it is not possible to blind clinicians or participants to their treatment allocation. Both treatments should be delivered within 18 weeks of randomisation (as per referral to treatment time), however where possible sites should deliver treatment within 12 weeks of randomisation. Participants will be followed up at 2 and 6 weeks post treatment and 3, 6, 12 and 24 months post treatment. A flow diagram illustrating the flow of participants through the study is presented in Appendix A.

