## 8. Analysis

All analyses will be conducted following intention to treat principles on a locked dataset using the latest available version of Stata. Continuous data will be summarised in terms of the non-missing sample size, mean, standard deviation, median, interquartile range and range, and categorical data will be summarised in terms of frequencies and proportions. The primary objective of the analysis is to investigate whether there is sufficient evidence to reject the hypothesis that outcomes (as measured by the 11 items in part 2 of the PEM) at 12 months post-treatment among patients randomised to collagenase are inferior to those of patients randomised to surgery, assuming a non-inferiority margin of 6 points. This assessment will be primarily based on whether the upper limit of the two-sided 95% CI for the difference between treatments at 12 months post treatment obtained from the primary analysis model (see Section 8.2) is greater than 6. One of the key secondary objectives is to compare the extent to which the correction achieved following treatment is maintained over the 12 months following treatment. This will be assessed by comparing rates of recurrence at 12 months post-treatment, where recurrence at 12 months is defined as a reduction in passive extension of 20 degrees between 3 and 12 months post-treatment (see Section 5.6.1). We will investigate whether there is sufficient evidence to reject the hypothesis that collagenase is inferior to surgery in terms of rates of recurrence at 12 months post-treatment, assuming a non-inferiority margin of 10%. This assessment will be based on whether the upper limits of the two-sided 95% CIs for the absolute differences in recurrence obtained from the fitted model (see Section 8.4.7) are less than 10%, and associated one-sided hypothesis tests of  $H_0: d \geq 10\%$ , where  $d = \Pr(\text{Recurrence} \mid \text{Collagenase}, X) - \Pr(\text{Recurrence} \mid \text{Surgery}, X)$  for various pre-specified representative covariate patterns  $X$ .

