#### **8.4.7 Recurrence**

Recurrence will be defined in a binary manner (recurred or not recurred) at 6, 12 and 24 months post-treatment. Recurrence at the 6 month follow up is defined as an increase in passive extension deficit of the reference joint of 6° since the 3 month post treatment follow up. Recurrence at 12 and 24 months is defined as an increase in passive extension deficit of the reference joint of 20° since the 3 month post treatment follow up. These binary outcomes will be modelled using mixed effect logistic regression models adjusting for study reference joint (MCP or PIP), study reference digit, baseline PEM score and baseline passive extension measurement as fixed effects with centre as a random effect. These models will include all participants for whom the relevant (i.e. month 6 or month 12) binary indicator of recurrence can be derived using the available data. If perfect prediction occurs due to empty strata at some covariate combinations, then participants with study reference digit indicated as middle, index or thumb will be pooled so that reference digit becomes a three category covariate (little, ring, other). If the issue persists, then the term for study reference digit will be dropped from the model. If the baseline PEM score and/or baseline passive extension measurement is missing, then they will be imputed using predicted values via regression of the observed values on observed baseline MHQ scores and reference joint (MCP or PIP). If the MHQ score is also missing, then missing baseline PEM scores and/or baseline passive extension measurements will be imputed using predicted values via regression of the observed values on the observed baseline URAM scores and reference joint. If baseline URAM score is also missing then missing baseline PEM scores and/or baseline passive extension measurements will be imputed with the reference joint strata specific means. For both analyses, the estimated odds ratios for allocation (and two-sided 95% CIs) will be reported. This model will also be used to derive the absolute differences in risk of recurrence (together with two-sided 95% CIs) at representative values of the covariates (mean of the continuous covariates, both levels of reference joint, two levels of reference digit (ring or little) and marginalising over the centre random effects). We will also test composite null hypotheses about the absolute difference in incidence of recurrence at 12

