and 24 months post-treatment. Specifically we will report one-sided p-values from four Wald tests of  $H_0: d \geq 10\%$  , where  $p < 0.025$  indicates statistical significance, and  $d = \Pr(\text{Recurrence} \mid \text{Collagenase}, X) - \Pr(\text{Recurrence} \mid \text{Surgery}, X)$  for the four covariate patterns  $X$  outlined above (MCP + Ring, MCP + Little, PIP + Ring, PIP + Little).

Due to the Coronavirus pandemic, a substantial proportion of participants were followed up remotely at 3, 6, 12 and 24 months post-treatment, and did not have goniometric measurements taken. Missingness due to remote follow up, as well as attrition, mean a substantial proportion of the post-treatment goniometric measurement data will be missing. The proportion of missing data at each time point will be summarised by randomised group, as will the available reasons this missing data. The principal analyses of recurrence outlined above (based on the available goniometric measurements) will be repeated using two alternative analysis sets. The first analysis set will supplement the available goniometric measurements with measurements obtained using photographs taken by clinical investigators. If photographs taken by the clinical investigators are not available, then measurements obtained using photographs taken by the participant will be used (note this would include photographs submitted by participants in the photography sub-study, as well as photographs submitted by non-sub-study participants who could not attend clinic visits due to the pandemic). The second analysis will use the multiply imputed dataset(s) generated as part of the analyses specified in Section 8.3.1. Both analysis sets will be analysed using the same models used for the analysis of the available goniometric measurements, with estimates and tests being reported analogously.

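### Each of the four recurrence non-inferiority tests in SAP 8.4.7 rejects more often than its stated one-sided 2.5% when recurrence is uncommon, because a Wald test is applied to a risk difference predicted at one covariate pattern.

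*SAP*

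**What the plan says.** SAP section 8 makes recurrence at 12 months part of a key secondary objective, with a non-inferiority margin of 10 percentage points. The criterion is "whether the upper limits of the two-sided 95% CIs for the absolute differences in recurrence obtained from the fitted model" lying below 10%, together with associated one-sided tests.

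Section 8.4.7 supplies the model: "These binary outcomes will be modelled using mixed effect logistic regression models adjusting for study reference joint (MCP or PIP), study reference digit". The PEM and passive extension values at baseline are further adjustment terms, and centre enters as a random effect. Differences are evaluated at the means of the continuous covariates, at "both levels of reference joint, two levels of reference digit (ring or little) and marginalising over the centre random effects". This gives four patterns (MCP or PIP, ring or little).

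The test is then named: "Specifically we will report one-sided p-values from four Wald tests of" the null hypothesis d ≥ 10% at each pattern, with p < 0.025 counted as significant. It applies at 12 and 24 months. The analysis is repeated on a photograph-supplemented set and on the multiply imputed data.

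The only provision for sparse data is to pool, and then if necessary drop, reference digit when perfect prediction occurs.

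**The concern.** The Wald standard error is evaluated at the estimated risks, not at the null. If collagenase shows few recurrences by chance, the estimated difference and its standard error fall together, so the upper limit drops below 10% more often than it should. The effect is strongest when events are few.

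Few events are plausible here. Recurrence at 12 months needs a 20° change after month 3, and 8.4.7 itself expects many goniometric measurements to be missing. The evaluable number is therefore likely to be below the 568 planned for the PEM.

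What is at stake is the 2.5% level attached to each pattern-specific statement of non-inferiority. The error runs in the direction that favours collagenase.

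**Working it through.** **The plan's own figures.** No sample size or power is stated for recurrence; the only relevant figure is the nominal 0.025. The PEM sample size reproduces: 2 × 22² × (1.960 + 1.2816)² / 6² = 282.5, so 283 per arm. With 284 per arm the t-test power is 90.05%, and 568 / 0.80 = 710.

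**Inputs from the SAP.** 1:1 allocation (section 2); margin 10 points (section 8); logistic model, four patterns, Wald tests, p < 0.025 (8.4.7).

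**Assumed inputs.** Surgery risk 3–15% at the tested pattern, with collagenase exactly 10 points higher. Evaluable total 300 or 568.

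**The statistic.** Let η₁ and η₀ be the predicted log-odds at pattern X for collagenase and surgery, p₁ and p₀ the corresponding risks, and V the covariance matrix of the coefficients. Then

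- d̂ = p₁ − p₀
- SE = √(g′Vg), with g = p₁(1−p₁)x₁ − p₀(1−p₀)x₀
- reject if (d̂ − 0.10)/SE < −1.96, which is the same as an upper Wald limit below 0.10.

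**Direction, in the simplest case.** Take two arms of 150 without covariates and true risks of 3% and 13%. The true SE is √(0.13×0.87/150 + 0.03×0.97/150) = 0.0308, so with that SE held fixed rejection needs d̂ below 0.10 − 1.96 × 0.0308 = 0.040. At d̂ = 0.040 (7% against 3%), the re-estimated SE is √(0.07×0.93/150 + 0.03×0.97/150) = 0.0251, and z = −0.060/0.0251 = −2.39. The Wald test has therefore already rejected at larger estimates.

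**Size.** Rejection rates at d = 10%. The pattern-specific columns are simulations of the fitted logistic model without a centre term; the two-arm columns are exact enumerations.

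| Surgery risk | Pattern Wald, 300 total | Pattern Wald, 568 total | Two-arm Wald, 150 per arm | Two-arm Wald, 284 per arm |
|---|---|---|---|---|
| 3% | 8.6–9.2% | 5.9–7.0% | 3.45% | 3.07% |
| 6% | 6.8–7.0% | 4.7–5.1% | 2.87% | 2.82% |
| 10% | 4.9–5.5% | 4.1–4.2% | 2.69% | 2.65% |
| 15% | 3.4% | 2.4–3.0% | 2.60% | 2.54% |

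A separate simulation with other seeds and covariate effects agrees. At a surgery risk of 5% it gives 7.5–8.6% (N = 284) and 5.1–6.6% (N = 568). At 20% it gives 2.9–3.3% and 2.3–3.3%. One cell with a centre SD of 0.3 in the generated data (N = 568, 5%) gives 6.0%. With 2,000 runs the Monte Carlo standard error at a true 2.5% is √(0.025×0.975/2000) = 0.35 points.

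**Where the excess comes from.** At 3% risk and 150 per arm, the two-arm test is 3.45 − 2.5 = 0.95 points too high. The pattern-specific test is 8.6 − 2.5 = 6.1 to 9.2 − 2.5 = 6.7 points too high. Most of the excess therefore comes from putting a symmetric delta-method interval on a risk predicted at one pattern. The risk-scale SE is roughly p(1−p) times the SE of η. In a plain arm, the SE of η rises as p falls, which offsets part of the shrinkage. At a pattern, part of the error in η comes from the joint, digit and continuous terms, whose precision depends on events elsewhere in the data. That offset is then weaker, and a prediction that is low by chance looks too precise.

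**Alternatives in the same model.** An upper limit from the logit-scale intervals (MOVER, formula under the fix) gives 1.9–2.9% across all pattern cells of the table, and 1.5–2.5% in the separate simulation. A constrained-likelihood test gives about 2.2–4.5%.

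**The case against.** **The rate is unknown.** The SAP gives no recurrence rate, and at 15–20% or more the planned test is nearly sound. This stands, and the point is conditional on it. But the rate cannot be known when the method is fixed, and a method that holds its level across the range costs little.

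**The combined claim.** A reader might infer that the recurrence objective as a whole is tested at 5–9%. The documents do not support that: 8.4.7 attaches p < 0.025 to each test and gives no rule for combining the four. If all four had to pass, one set of runs gave at most 1.4%. Another gave 0.3–2.2% with equal-risk patterns and 2.4–3.7% when only the highest-risk pattern sat on the margin.

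**The Wald method as such.** A reader might also blame any Wald test of a risk difference and substitute a joint-stratified Miettinen-Nurminen interval. The two-arm columns show that a plain Wald test is only about 1 point off at most at these risks and sizes. The stratified interval targets one overall difference and drops the planned covariate adjustment, so it answers a different question.

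**The confidence intervals.** The SAP names Wald for the tests. For the limits, section 8 and 8.4.7 say only that they are two-sided 95% ("This model will also be used to derive the absolute differences in risk of recurrence (together with two-sided 95% CIs"). That these too are Wald is an inference. If they are not, interval and test could disagree at the margin, which is itself a reason to name the method.

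**No computable statistic.** Failure through an arm without events is a corner case: up to about 5% of runs at 150 per arm and 3% risk, and at most 0.24% at 284 per arm. The point does not rest on it.

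**Imputed data.** Wald estimates pool directly by Rubin's rules, so a replacement must be poolable too. The fix provides for this.

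**Conclusion.** The point holds for each single test. At d = 10%, the planned Wald test at a covariate pattern rejects about 5–9% of the time (surgery risk 3–10%, about 300 evaluable in total) or about 4–7% (568 evaluable), against a stated 2.5%. From a surgery risk of about 15–20% upward it is close to nominal, about 2.4–3.4%; one set of runs reached 3.8% at 15% risk and 150 per arm.

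These figures rest on an assumed recurrence rate and evaluable number, and on fitted models without the centre term. The direction is well established; the size in this trial is not known. No inflated error is shown for a conclusion drawn from all four tests together. Recurrence is secondary, and the PEM non-inferiority conclusion is not touched. It should be corrected, but it does not threaten the trial's main result.

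**What to change.** In sections 8 and 8.4.7, keep the mixed logistic model, the four patterns, the 10-point margin and the odds ratio as planned. Replace the Wald tests, and any Wald limits for the risk difference, by a named upper limit that respects the probability scale. Declare non-inferiority at a pattern only if that limit is below 10%. Two options:

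- **MOVER on the logit scale.** With u₁ the upper 95% logit-based limit for p₁, l₀ the lower one for p₀, and r the correlation of the two predicted log-odds, the upper limit is d̂ + √[(u₁ − p₁)² + (p₀ − l₀)² − 2r(u₁ − p₁)(p₀ − l₀)].
- **A constrained-likelihood limit.** This is harder to program for a mixed model and less exact in these settings (about 2.2–4.5%).

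For the multiply imputed set, pool the two predicted log-odds and their covariance by Rubin's rules, then form the same limit. A joint-stratified Miettinen-Nurminen interval for one overall difference may be added as supportive, not as a replacement.

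The cost is SAP wording and, for the MOVER limit, modest programming. Upper limits become slightly wider and power for recurrence non-inferiority slightly lower.

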### 5.6.1 Recurrence

Recurrence at 6 months is defined as a change in extension deficit (measured as passive extension) of the reference joint of 6° or greater between 3 and 6 months post treatment. Recurrence at 12 months is defined as a change in extension deficit (measured as passive extension) of 20° or greater between 3 and 12 months post treatment [6]. This definition will be used to compare recurrence in each arm at 6 and 12 months post treatment.

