### 5.9 Photographs in clinic

Three photographs of participants' hands will be collected at baseline and 3, 6, 12 and 24 months post treatment as follows

- A photograph of the reference hand in extension, taken directly above the hand (anterior view)
- A photograph of the reference hand in extension, taken from the side with the little finger closest to the camera
- A photograph of the reference hand in flexion, taken from the side with the little finger closest to the camera

These images will be used to obtain further measurements of active extension and flexion of the reference digit at each time point. The joint measurements obtained using these images will be used to validate and supplement goniometric measurements and will also be used for secondary analyses in the photography sub study.

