## **5.10 Participant photographs**

Participants consenting to the photography sub study are shown how to take the required photographs (the same images as taken in clinic) of their hand at baseline and provided with detailed instructions. Sub study participants are asked to take standardised photographs of their study reference hand at baseline (as soon after the baseline visit as possible) and 3, 6, 12 and 24 months post treatment, which are then sent to the study team. Assessing the agreement between the goniometric measurements and measurements obtained using these images will be the primary goal of the photography sub study.

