Passive RoM	
3 Months	
6 Months	
12 Months	
24 Months	

**Table xx:** Estimated differences in RoM at each post-treatment time point (Goniometer and photographic measurements)

	Estimated difference (95% CI)
Active RoM	
3 Months	
6 Months	
12 Months	
24 Months	
Passive RoM	
3 Months	
6 Months	
12 Months	
24 Months	

**Table xx:** Estimated differences in RoM at each post-treatment time point (multiply imputed data)

	Estimated difference (95% CI)
Active RoM	
3 Months	
6 Months	
12 Months	
24 Months	
Passive RoM	
3 Months	
6 Months	
12 Months	
24 Months	

**Table xx:** Treatment complications by randomised group (worst single treatment complication experienced)

Level	Collagenase (N = )	Surgery (N = )	Total (N = )
None (0)			
Technical – not complication (1)			
Very minor (2)			
Mild (3)			
Moderate (4)			
Severe (5)			
Devastating (6)			
Death (7)			

**Table xx:** Estimated absolute differences in proportions experiencing complication of level  $j$  or higher, for  $j = 1, \dots, 7$  from fitted proportional odds model

Covariate values (X)	Level	Absolute difference (95% CI) ( $\Pr(Y \geq j   \text{collagenase, X}) - \Pr(Y \geq j   \text{surgery, X})$ )
Joint = MCP Digit = Ring PEM = mean	$j = 1$ (Technical)	
Joint = MCP Digit = Little PEM = mean	$j = 1$ (Technical)	
Joint = PIP Digit = Ring PEM = mean	$j = 1$ (Technical)	
Joint = PIP Digit = Little PEM = mean	$j = 1$ (Technical)	
Joint = MCP Digit = Ring PEM = mean	$j = 2$ (Very minor)	
Joint = MCP Digit = Little PEM = mean	$j = 2$ (Very minor)	
Joint = PIP Digit = Ring PEM = mean	$j = 2$ (Very minor)	
Joint = PIP Digit = Little PEM = mean	$j = 2$ (Very minor)	

**Table xx:** Odds ratios for allocation for each level  $j = 1, \dots, 7$  from partial proportional odds model

Level	Odds ratio for allocation (95% CI)
$j = 1$ (Technical)	
$j = 2$ (Very minor)	
$j = 3$ (Mild)	
$j = 4$ (Moderate)	
$j = 5$ (Severe)	
$j = 6$ (Devastating)	
$j = 7$ (Death)	

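### The photo-supplemented repeats of recurrence and passive RoM put active-extension readings into outcomes defined on passive extension

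*SAP*

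**What the plan says.** Outcome definition. SAP 5.6.1 defines 12-month recurrence as a "change in extension deficit (measured as passive extension) of 20° or greater between 3 and 12 months post treatment". Section 8.4.7 also uses passive extension deficit, with thresholds of 6° at 6 months and 20° at 12 and 24 months, each measured from month 3. Table 1 and section 5.6.2 keep active and passive extension apart and derive an active and a passive RoM.

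What the photographs measure. On the clinic photographs, section 5.9 says: "These images will be used to obtain further measurements of active extension and flexion of the reference digit at each time point". Participant photographs are "the same images as taken in clinic" (5.10). Passive extension is not listed for either.

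How the photographs are used. Section 5.9 says that the photo measurements "will be used to validate and supplement goniometric measurements". Sections 8.4.7 and 8.4.8 repeat the principal analyses on a supplemented set: "The first analysis set will supplement the available goniometric measurements with measurements obtained using photographs taken by clinical investigators". Participant photographs are used where clinic ones are unavailable. The same models are fitted and the results reported in the same way, including the one-sided tests against 10% at 12 and 24 months. Appendix F has a table titled "Estimated differences in RoM at each post-treatment time point (Goniometer and photographic measurements" with a passive RoM block. The other repeat is by imputation: "The second analysis will use the multiply imputed dataset(s) generated as part of the analyses specified in Section 8.3.1".

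**The concern.** Recurrence takes only passive extension as its input, so every photo value that enters it is an active value. Assuming that a joint actively extends no further than it can be moved passively, the active deficit is at least as large as the passive one. A passive goniometer reading at month 3 followed by a photograph adds the gap to the change; the reverse order subtracts it. Because recurrence is a thresholded change, the gap turns directly into false or missed recurrences. Passive RoM has the same mixture without the threshold.

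The supplemented set exists because the SAP expects much of the goniometry to be missing after the pandemic. Readers will treat it as a robustness check on a key secondary objective that has its own non-inferiority margin. If it agrees or disagrees with the principal analysis because two quantities were mixed, it does not serve that purpose.

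**Working it through.** The SAP gives no figure to reproduce on this point. The check is a comparison of text, followed by an illustration of size.

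**Text.**

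- Recurrence needs passive extension at month 3 and at the later visit (5.6.1, 8.4.7). Photographs supply active extension (5.9, 5.10). The two do not match.
- Passive RoM needs passive extension and flexion (5.6.2). Photographs supply the flexion but not the passive extension. The Appendix F table still has passive RoM rows.
- Active extension, active RoM and flexion (8.4.8 to 8.4.10) need only what photographs supply. These match.
- Sections 8.4.7 and 8.4.8 give no rule that both visits use the same mode (active or passive), no calibration and no term for the source of the measurement.
- The photography sub-study (8.7) plans agreement for participant photographs at baseline, 3 and 6 months and for clinic photographs at baseline. It covers neither 12 nor 24 months, and its results are not carried into the supplemented sets.

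**Size.** Inputs from the SAP are the 20° threshold and the 10-point margin. Assumptions not in the SAP are a constant gap g (active minus passive deficit) of 0° to 15° and a normal true passive change with mean μ = 3° and SD σ = 8°.

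P(recurrence) = 1 − Φ((20 − s − μ)/σ), with s = 0 for the same mode at both visits, s = +g for goniometer then photo, and s = −g for photo then goniometer.

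- Same mode: 1 − Φ(17/8) = 1.7%.
- g = 10°, goniometer then photo: 1 − Φ(7/8) = 19.1%.
- g = 10°, photo then goniometer: 1 − Φ(27/8) = 0.0%.

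| Gap g | Same mode | Goniometer then photo | Photo then goniometer |
|---|---|---|---|
| 0° | 1.7% | 1.7% | 1.7% |
| 5° | 1.7% | 6.7% | 0.3% |
| 10° | 1.7% | 19.1% | 0.0% |
| 15° | 1.7% | 40.1% | 0.0% |

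With other assumed change distributions at g = 10°, goniometer-then-photo moves recurrence from 0.0% to 2.3% (mean 0°, SD 5°) or from 6.7% to 30.9% (mean 5°, SD 10°).

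**Effect on the arm comparison.** With no true difference and the same gap in both arms, the spurious difference is (f1 − f0) × (P_switch − P_same), where f1 and f0 are the proportions switching in each arm. Assume 40% and 20%, goniometer then photo:

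- g = 5°: 0.20 × (6.7 − 1.7) = 1.0 point.
- g = 10°: 0.20 × (19.1 − 1.7) = 3.5 points.
- g = 15°: 0.20 × (40.1 − 1.7) = 7.7 points.
- g = 10°, photo then goniometer: 0.20 × (0.0 − 1.7) = −0.3 points.
- Equal switching: zero at any g, although the rates themselves are distorted.

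If photographs are used at both visits, a stable gap cancels. The result is then active-extension recurrence, which is not the defined outcome.

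**The case against.** The strongest reply is that little depends on these analyses. Section 8.4.7 names the goniometer-only analyses as principal, and the photo set is one of two repeats. The other repeat imputes passive extension as passive extension (Table 3) and mixes no modes. This stands, and it limits how serious the point is.

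The size is also open to challenge. The gap and the change distribution are assumptions, and the rates apply to joints that switched mode, not to the whole trial. The 6-month 6° rule gives larger shifts (35.4% to 80.9% at g = 10° under the main assumptions), but the 10% tests are at 12 and 24 months, where the 20° rule applies. The 6-month figures therefore say nothing about non-inferiority. This stands too.

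A reader might infer that the longer wait for surgery makes switching unequal and so biases the recurrence test. The SAP does not establish this. It does not say that remote follow-up differs by arm, section 2 plans both treatments within 18 weeks of randomisation, and follow-up is timed from treatment. Missing goniometry and its reasons will be summarised by group, which would show an imbalance in missingness.

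Finally, supplementation might be meant like for like, active with active. That reading works for active RoM, active extension and flexion. It cannot work for recurrence, which has no active input, and the passive RoM rows in Appendix F contradict it.

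**Conclusion.** The rule is wrong as written and should be fixed, but its reach is limited to the photo-supplemented repeats of recurrence (8.4.7) and passive RoM (8.4.8, Appendix F). A reader might conclude that the trial's recurrence non-inferiority test, or its primary result, is compromised. The documents do not support that, because the principal recurrence and RoM analyses use goniometer data only and PEM does not involve joint measurement.

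The text conflict is certain. The direction of the error in one joint follows from the order of the modes, given that the active deficit is at least the passive one. Its size depends on a gap that the SAP does not give, and at a gap of zero there is no effect. With no true difference, a spurious difference between arms also needs unequal switching or an unequal gap. Under the stated assumptions it is about 3.5 points at a 10° gap, and 1.0 to 7.7 points over gaps of 5° to 15°, against a margin of 10.

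**What to change.** 1. State in 8.4.7 and 8.4.8 that photo values supplement only active extension, active RoM and flexion.
2. Remove passive RoM from the supplemented set and from its Appendix F table.
3. Either drop supplemented recurrence, or report it as a separately labelled active-extension outcome with active measurements, by goniometer or photograph, at both month 3 and the later visit. Do not present it as a repeat of the passive-recurrence non-inferiority test, and relabel or delete the supplemented rows of the Appendix F recurrence table.
4. Optionally, use photo-derived active extension as an auxiliary variable in a separate imputation for passive recurrence. Leave the Table 3 model as it is, because it also feeds the sensitivity analysis of the primary outcome.

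Steps 1 to 3 are changes to wording, tables and the derivation of one outcome, and need no new data, since active goniometry is already scheduled at every relevant visit (Table 1). The cost is that fewer participants contribute to supplemented recurrence. Step 4 adds a second imputation model to specify and check.
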